13.3. Sample Size Sensitivity

13.3.1. Sample Size Re-estimation

Sample size re-estimation is not planned for this study.

13.4. Data Analysis Considerations

Data will be listed and summarized according to GSK integrated data standards library (IDSL) reporting standards and the Clinical Data Interchange Standards Consortium (CDISC) where applicable. Complete details will be provided in the Reporting and Analysis Plan (RAP).

13.4.1. Analysis Populations

The ‘All Treated’ population is defined as all eligible subjects who receive at least 1 dose of study treatment. An incorrect treatment schedule or drug administration or an early termination of treatment will not result in exclusion of subjects from this population. Subjects with major deviations from the eligibility criteria affecting safety or from the treatment schedule at the DLT evaluation period (1 cycle: 21 days for once every 3 weeks schedule or 28 days for once weekly schedule) for reasons other than toxicity may be presented in separate tables/listings.

The ‘All Treated’ population will further be classified in the following sub-populations.

- Part 1: all Part 1 subjects of All Treated population. Note, subjects in Part 1 are exclusively multiple myeloma patients.
- Part 2 MM: all Part 2 MM subjects of All Treated population
- All Treated MM: comprise of subjects in Part 1 and Part 2 MM.
- Part 2 NHL: all Part 2 lymphoma subjects of All Treated population.

The ‘**DLT Evaluable**’ population in Part 1 enables an appropriate evaluation of study DLTs. It is defined as those subjects fulfilling the ‘All Treated’ population criteria, and having met the following adequate exposure criteria:

- For Schedule 1 (once every 3 weeks dosing) subjects received a complete infusion in cycle 1.
- For Schedule 2 (once weekly dosing for 3 consecutive weeks, 1 week rest) subjects receive three infusions, two of which must be complete infusions, in cycle 1. (as increases up to $\leq 30\%$ are implemented between cohorts, less than 2 complete infusions would result in a total dose closer to the previous dose investigated).

Any subject in the “All Treated” population who experiences a DLT, as defined in Section 3.3.3 will also be included in the DLT evaluable population regardless of exposure.

The ‘**Evaluable (MM)**’ population is a subset of the ‘All Treated’ population, who were initially treated at RP2D in the expansion cohort and have at least two post-baseline disease assessments or they have progressed or died or permanently discontinued treatment. This population will be used for the futility analysis of the MM expansion cohort.

The ‘**Pharmacokinetic (PK) Population**’ is defined as those subjects in the “All Treated” population from whom at least one PK sample was obtained, analyzed, and was measurable.

The ‘**Pharmacodynamic (PD) Population**’ is defined as those subjects in the “All Treated” population from whom at least one PD sample was obtained, analyzed, and was measurable.

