7.1.2. Dose Expansion

7.1.2.1. Every 3 Weeks Dosing Schedule for Multiple Myeloma

	Time and Events Table for Full Study (Cycle = 21 days)								
Study Assessments ¹	Screen ²	Day 1 C1	Day 8 C1	Day 15 C1	Day 1 C2	D1 of C3-C16	End of Study Treatment ³⁴	Monthly Follow up ³⁵	
Baseline Demographics	X								
Medical History	X								
Physical Exam	X	X			X	At the start of each cycle	X		
Ocular Exam	X ³				X ⁴	At the start of each cycle ⁴	X ⁴	X ³⁵	
ECOG Performance Status	X				X	At the start of each cycle	X		
Vital Signs (BP, HR, Body Temperature)	X	X ⁵	X	X	X ⁵	At the start of each cycle ⁵	X		
Weight and Height	X	Weight only			Weight only	Weight only - At the start of each cycle	Weight only		
Hematology	X	X ⁶	X	X	X	At the start of each cycle	X		
Clinical chemistry	X	X ⁶	X	X	X	At the start of each cycle	X		
Urine Dipstick	X	X ⁶			X	At the start of each cycle	X		
INR, PTT	X	X ⁶	X	X	X	At the start of each cycle			
HBV/HCV tests	X								
CK-MB , Troponin	X ^{7,8}		X ^{7,8}		X ^{7,8}	At the start of each cycle ^{7,8}	X ^{7,8}		
BNP	X ⁹								
UPEP and urine Immunofixation	X				X	At the start of each cycle			
SPEP and serum immunofixation and Serum M-protein Calculation	X				X	At the start of each cycle			
Kappa, lambda free LC, FLC ratio	X				X	At the start of each cycle			

Time and Events Table for Full Study (Cycle = 21 days)									
Study Assessments ¹	Screen ²	Day 1 C1	Day 8 C1	Day 15 C1	Day 1 C2	D1 of C3-C16	End of Study Treatment ³⁴	Monthly Follow up ³⁵	
24 hr urine protein and albumin	X				X	At the start of each cycle			
IgG, IgM, IgA	X				X	At the start of each cycle			
CRP, beta2 microglobulin	X				X	At the start of each cycle			
Pregnancy Test	X ¹⁰					At the start of cycles 5 ¹⁰ , 9 ¹⁰ , 13 ¹⁰	X ¹⁰	X ¹¹	
Chest X-ray	X								
12-lead ECG	X ¹²	X ¹²	X ¹²	X ¹²	X ¹²	At the start of each cycle ¹²	X ¹²		
LVEF and valves assessment (ECHO)	X ¹³					At the start of cycles 4 ¹³ , 9 ¹³	X ¹³		
Extramedullary Plasmacytoma Imaging	X ¹⁴					At the start of cycles 5 ¹⁴ , 9 ¹⁴ , 13 ¹⁴	X ¹⁴		
BM Aspirate (see below for each test required within procedure):									
Disease assessment	X ¹⁵					At the time of Complete Response			
BCMA assessment and PD (flow)	X ¹⁶		X ^{16, 18}						
FISH testing	X ¹⁷								
BM biopsy for disease assessment	X ¹⁹					At the time of CR (disease assessment only)			
Serum (soluble BCMA)		X ²⁰			X ²⁰	Predose at the start of each cycle	X		
Serum (cytokines/chemokines)		X ²¹			X ²¹	Predose and EOI on D1 of each cycle	X		

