- If completed within 72 hrs prior to the first dose, this assessment need not be repeated on Day 1 of Cycle 1. Refer to [Table 15](#) for a comprehensive list of lab tests.
- Troponin will be measured at the local (troponin I or T) and central (troponin I) lab.
- CK-MB at the local lab or if not available by a central laboratory.
- BNP to be measured locally, or if not available by a central laboratory, at screening; if cardiac workup is required due to safety concerns during the study, BNP should be measured.

10. Perform only in women of child-bearing potential. A serum pregnancy test should be performed at screening, and subsequent pregnancy tests may be either serum or urine.
11. Final pregnancy test (serum or urine) must be performed in women of childbearing potential 60 days after last study treatment.
12. ECGs to be performed in triplicate. On dosing days, ECG to be performed at predose (within 30 minutes prior to SOI) and EOI. At screening, on interim visits (C1D8 and C1D15) and End of Study, obtain a single ECG measurement. **On days where ECG timepoints align with PK sampling timepoints, ECGs should be performed prior to PK samples being drawn (PK sample should be taken at the exact nominal time; refer to footnote 24)**
13. At Screening, LVEF may be performed within 30 days prior to first dose. All ECHOs indicated on dosing days may be performed up to 5 days before dosing. ECHOs to be done locally and sent to GSK for central imaging storage.
14. May be performed up to 21 days prior to C1D1 as screening value. Needs to be performed with the same method throughout the study as was done at baseline (i.e. if PET scan was used as baseline, subject needs to be followed by PET scans). Selected target lesion needs to be measured and followed over time.
15. Samples from within 14 days prior to first dose are acceptable.
16. Sample(s) collected for analysis at central lab. The same sample will be used for BCMA (flow) and PD. On D8 only postdose PD assessment will be performed, if applicable (refer to footnote 18).
17. FISH testing at least for: t(4;14), t(14;16), 17p13del. FISH results from samples taken within 60 days prior to first dose are acceptable.
18. **Additional samples may be collected in some subjects (up to 6) for further exploration of PD.**
19. Archival tissue from up to 60 days prior to study is acceptable.

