7.7. Evaluation of Anti-Cancer Activity

Standard disease assessments for MM will include laboratory tests, bone marrow aspirate (cytology, flow cytometry, FLC, etc.) and Bone Marrow biopsy for BCMA expression (IHC) during screening and at the time of CR. Evaluation will be according to the International Myeloma Working Group Uniform Response Criteria for Multiple Myeloma ([Appendix 1](#)). Disease assessment for subjects with lymphomas will be evaluated at screening and every 9 weeks (for subjects on every 3 week dosing schedule) or every 8 weeks (for subjects on weekly dosing schedule), and at the end of study. Disease assessment for subjects with lymphomas will be according to the Revised Response Criteria for Malignant Lymphoma ([Appendix 2](#)).

- Clinical activity measured as Overall Response Rate (ORR) which is defined as follows:
 - For MM: the percentage of subjects with confirmed stringent complete response (sCR), complete response (CR), very good partial response (VGPR), and partial response (PR) as assessed by 2011 recommendation of the International Myeloma Working Group (IMWG) Panel I ([Appendix 1](#)). Other comparisons of interest may be considered (see Section [13.5.2](#))

- For lymphomas: the percentage of subjects with confirmed CR, PR, as described in the Revised Response Criteria for Malignant Lymphoma ([Appendix 2](#)).

Disease assessment may include imaging (e.g., computed tomography [CT] scan, magnetic resonance imaging [MRI], bone scan, plain radiography) and physical examination (as indicated for palpable/superficial lesions). Disease assessment will be completed within 4 weeks prior to the first dose of GSK2857916 then every 8 or 9 weeks thereafter, and at the final study visit. See the Time and Events Tables (Section 7.1) for the schedule of assessments of anti-cancer activity. Assessments must be performed on a calendar schedule and should not be affected by dose interruptions/delays. For post-baseline assessments, a window of ± 3 days is permitted to allow for flexible scheduling with the exception of dose administration days where a window of ± 3 days for Schedule 1 (once every 3 weeks) is permitted and ± 1 day for Schedule 2 (weekly) is permitted. If the last radiographic assessment was more than 8 or 9 weeks prior to the subject's withdrawal from study and progressive disease has not been documented, a disease assessment should be obtained at the time of withdrawal from study.

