13.6. Interim Analysis

13.6.1. Part 1

While no formal interim analysis is planned for Part 1, safety, pharmacokinetic and pharmacodynamic marker data will be examined on an ongoing basis to support dose escalation decisions. Prior to determining the GSK2857916 dose for the next cohort enrolled, exploratory analysis will be conducted to assess the relationship of GSK2857916 dose levels with safety, PK and PD parameters using all data from available cohorts. For more details of the dose escalation procedure, see Section 3.3.

13.6.2. Part 2

The methodology utilized is based on the predictive probability of success if enrollment continues to 40 subjects [Lee, 2008]. The predictive probability design is similar to a Green-Dahlberg design in that it allows for early stopping for futility. The differences are that the predictive probability design allows for evaluation of stopping rules as often as after each subject, rather than at only two stages. While the two designs have similar type I and type II error rates, the probability of early termination is greater with the predictive probability design. In this particular study, we will stop only for futility and evaluate the stopping rules once approximately 15, 22, and 30 subjects are evaluable (though additional futility looks are also controlled for if necessary). A subject is considered evaluable if they are in the all treated population and have had at least two post baseline disease assessments.

For the MM expansion cohort, response data will be reviewed once approximately 15, 22, and 30 subjects are evaluable and the number of overall responses (PR, VGPR, CR, and sCR) observed will be compared with the stopping rules provided in Table 17 below.

Table 17 Futility Stopping Region

Number of Evaluable Subjects	Number of Overall Responses												
	0	1	2	3	4	5	6	7	8	9	10	11	>11
15	Shaded	Shaded	Shaded										
16	Shaded	Shaded	Shaded										
17	Shaded	Shaded	Shaded										
18	Shaded	Shaded	Shaded	Shaded									
19	Shaded	Shaded	Shaded	Shaded									
20	Shaded	Shaded	Shaded	Shaded									
21	Shaded	Shaded	Shaded	Shaded									
22	Shaded	Shaded	Shaded	Shaded	Shaded								
23	Shaded	Shaded	Shaded	Shaded	Shaded								
24	Shaded	Shaded	Shaded	Shaded	Shaded								
25	Shaded	Shaded	Shaded	Shaded	Shaded	Shaded							
26	Shaded	Shaded	Shaded	Shaded	Shaded	Shaded							
27	Shaded	Shaded	Shaded	Shaded	Shaded	Shaded							
28	Shaded	Shaded	Shaded	Shaded	Shaded	Shaded							

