29	Shaded	Shaded	Shaded	Shaded	Shaded	Shaded	Shaded						
30	Shaded	Shaded	Shaded	Shaded	Shaded	Shaded	Shaded						
31	Shaded	Shaded	Shaded	Shaded	Shaded	Shaded	Shaded						
32	Shaded	Shaded	Shaded	Shaded	Shaded	Shaded	Shaded	Shaded					
33	Shaded	Shaded	Shaded	Shaded	Shaded	Shaded	Shaded	Shaded	Shaded				
34	Shaded	Shaded	Shaded	Shaded	Shaded	Shaded	Shaded	Shaded	Shaded	Shaded			
35	Shaded	Shaded	Shaded	Shaded	Shaded	Shaded	Shaded	Shaded	Shaded	Shaded			
36	Shaded	Shaded	Shaded	Shaded	Shaded	Shaded	Shaded	Shaded	Shaded	Shaded			
37	Shaded	Shaded	Shaded	Shaded	Shaded	Shaded	Shaded	Shaded	Shaded	Shaded	Shaded		
38	Shaded	Shaded	Shaded	Shaded	Shaded	Shaded	Shaded	Shaded	Shaded	Shaded	Shaded		
39	Shaded	Shaded	Shaded	Shaded	Shaded	Shaded	Shaded	Shaded	Shaded	Shaded	Shaded	Shaded	
40	Shaded	Shaded	Shaded	Shaded	Shaded	Shaded	Shaded	Shaded	Shaded	Shaded	Shaded	Shaded	Shaded

Note: The shaded regions are the specific regions for stopping the study for futility. For instance, if there are 4-5 or fewer responses in 25 subjects, then the predictive probability for success will be less than the futility criterion, 5.0%, and the study will be stopped.

In addition to the considering the recommendations of the futility analyses, final decisions on stopping enrolment in the MM cohort will depend on the totality of the data collected. Examples of consideration of the totality of the data include, further investigation of the clinical activity of subgroups of subjects based on their BCMA expression levels and evaluation of the quality of responses (including sCR, CR and Clinical Benefit Rate, as defined in [Appendix 1](#)). Should the recommendation to stop for futility be disregarded in favor of a decision to continue the trial based on the totality of the data, the overall type I error rate of the expansion phase will be inflated.

No interim analyses will be performed on the BCMA+ lymphomas cohort; though consideration would be given to closing the cohort should the enrollment be stopped in the MM cohort.

If necessary, a subject may be replaced if they are deemed to be Lost to Follow-Up (LTFU) or they have withdrawn due to a toxicity deemed to not have been related to GSK2857916.

Subjects will not be replaced when they discontinue the study due to: Progression (symptomatic or otherwise), toxicity related to GSK2857916, or lack of efficacy.

Other administrative interim analyses may be performed if needed.

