16. APPENDICES

16.1. Appendix 1: International Myeloma Working Group Uniform Response Criteria for Multiple Myeloma

Response	IMWG Criteria
sCR	
 CR as defined below plus normal FLC ratio and absence of clonal cells in bone marrow³ by immunohistochemistry or immunofluorescence⁴
CR	
 Negative immunofixation on the serum and urine and disappearance of any soft tissue plasmacytomas and < 5% plasma cells in bone marrow³
VGPR	
 Serum and urine M-protein detectable by immunofixation but not on electrophoresis 
or
 
 ≥ 90% reduction in serum M-protein plus urine M-protein level <100 mg/24 h
PR	
 ≥ 50% reduction of serum M-protein and reduction in 24 hours urinary M-protein by ≥90% or to < 200 mg/24 h If the serum and urine M-protein are unmeasurable,⁵ a ≥ 50% decrease in the difference between involved and uninvolved FLC levels is required in place of the M-protein criteria If serum and urine M-protein are not measurable, and serum free light assay is also not measurable, ≥ 50% reduction in plasma cells is required in place of M-protein, provided baseline bone marrow plasma cell percentage was ≥ 30% In addition to the above listed criteria, if present at baseline, a ≥ 50% reduction in the size of soft tissue plasmacytomas is also required
MR	
 ≥25% but <49% reduction of serum M protein and reduction in 24 hour urine M protein by 50-89%, which still exceeds 200 mg per 24 hour In addition to the above criteria, if present at baseline, 25-49% reduction in the size of soft tissue plasmacytomas is also required No increase in size or number of lytic bone lesions (development of compression fracture does not exclude response)
No change/Stable disease	
 Not meeting criteria for CR, VGPR, PR, or progressive disease
Progressive Disease	
 Increase of ≥ 25% from lowest response value in any one or more of the following: 
 ○ Serum M-component and/or (the absolute increase must be ≥ 0.5 g/dL)⁶ ○ Urine M-component and/or (the absolute increase must be ≥200 mg/24 h)

Response	IMWG Criteria

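### A myeloma subject with a baseline plasmacytoma can enter the futility count at C3D1, before the first scheduled image at C5D1 can show a partial response

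*Protocol*

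**What the plan says.** Two places in the protocol define who counts at a futility look.

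- Section 13.4.1, Evaluable (MM): expansion subjects treated at the RP2D who "have at least two post-baseline disease assessments or they have progressed or died or permanently discontinued treatment". This population is assigned to the futility analysis.
- Section 13.6.2: "A subject is considered evaluable if they are in the all treated population and have had at least two post baseline disease assessments". The clause on progression, death and discontinuation is absent here.

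Neither refers to plasmacytoma imaging. Four other places decide what this means for a subject with a plasmacytoma.

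- Section 7.7: "Standard disease assessments for MM will include laboratory tests". The MM tables (7.1.2.1 and 7.1.2.2) schedule M-protein and free light chain tests at C2D1 and at the start of each later cycle.
- The same tables schedule "Extramedullary Plasmacytoma Imaging" at screening, at the start of cycles 5, 9 and 13, and at end of treatment. The footnote adds: "Needs to be performed with the same method throughout the study as was done at baseline".
- Appendix 1, PR: if a plasmacytoma was present at baseline, a 50% or greater "reduction in the size of soft tissue plasmacytomas is also required".
- Section 7.7 also has a general sentence placing disease assessment within 4 weeks before first dose and "then every 8 or 9 weeks thereafter". It is not limited to lymphoma.

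On the outcome of a look, Section 13.6.2 says that "final decisions on stopping enrolment in the MM cohort will depend on the totality of the data collected".

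**The concern.** The stopping limits in Table 17 treat the response of each evaluable subject as known. On the per-cycle reading, an ongoing subject with a baseline plasmacytoma enters the denominator at C3D1, while scheduled data cannot support PR until C5D1. Any such subject who is truly responding is counted as a non-responder at that look. The clearest case is a subject who qualified on a biopsy-proven plasmacytoma alone, which inclusion criterion 4 allows.

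The error can only remove responders, so it pushes one way: towards recommending that an active drug be stopped. It does not inflate the type I error.

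**Working it through.** **1. The window**

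| | C3D1 (second laboratory assessment) | C5D1 (first scheduled image) | Gap |
|---|---|---|---|
| Every 3 weeks | 2 × 21 days = week 6 | 4 × 21 days = week 12 | 6 weeks |
| Weekly dosing (28-day cycle) | 2 × 28 days = week 8 | 4 × 28 days = week 16 | 8 weeks |

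**2. Reproducing the plan's figures (Section 13.2.2)**

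Inputs: Beta(0.25, 0.75) prior, stop if the predictive probability of success is below 5%, maximum 40 subjects, a look after every subject from 15 to 39. Success is taken as 12 or more responders of 40, the value that reproduces the stated results.

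| | Stated | Recomputed |
|---|---|---|
| Type I error | 0.075 | 0.0754 |
| Power | 89.8% | 89.75% |
| Early termination at 20% / 40% | 88.9% / 8.5% | 88.85% / 8.49% |
| Expected N at 20% / 40% | 23.4 / 38.6 | 23.42 / 38.64 |

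The recomputed limits at the planned looks are 2 or fewer of 15, 4 or fewer of 22 and 6 or fewer of 30, as in Table 17.

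**3. Three planned looks, no imaging lag, ORR 40%**

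First look: P(X ≤ 2 | 15, 0.4) = 0.6^15 + 15(0.4)(0.6^14) + 105(0.4²)(0.6^13) = 0.0005 + 0.0047 + 0.0219 = 2.7%. The exact sequential calculation adds 1.4% at 22 and 0.5% at 30. The total is 4.6%, with power 90.8%.

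**4. How many subjects are in the window**

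A look is held when the nth subject reaches C3D1. On the three-weekly schedule the number not yet at C5D1 is about 6 weeks × accrual rate, plus the subject who triggers the look: 3 + 1 = 4 at 0.5 per week, 6 + 1 = 7 at 1 per week, and 12 to 13 at 2 per week. With 7 in the window, a 20% plasmacytoma share and ORR 40%, the expected number of hidden responders is 7 × 0.2 × 0.4 = 0.56. At the first look that is out of an expected 15 × 0.4 = 6.

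**5. Effect on the futility recommendation**

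Simulation with 200,000 trials per cell and Poisson accrual without pause. Responders without a plasmacytoma are counted at C3D1, and responders with one only from C5D1. Entries are the chance of crossing a limit at any of the three looks, at ORR 40%, for plasmacytoma shares of 10 / 20 / 30%.

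| Accrual | Every 3 weeks | Weekly dosing |
|---|---|---|
| 0.5 per week | 5.5 / 6.4 / 7.4% | 5.7 / 6.9 / 8.4% |
| 1 per week | 6.1 / 8.1 / 10.7% | 6.7 / 9.4 / 13.0% |
| 2 per week | 7.6 / 11.9 / 18.4% | 8.4 / 14.4 / 23.1% |

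A version without an accrual model fixes the fraction of evaluable subjects in the window. With one third in the window, the false stop is 6.0 / 7.6 / 9.4% and power 89.8 / 88.6 / 87.3%. With two thirds, it is 7.6 / 12.2 / 18.6% and power 88.6 / 84.8 / 79.3%. At ORR 20% the type I error does not rise: it goes from about 0.08 to between 0.04 and 0.08.

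**6. The other reading**

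If MM assessments fall every 8 or 9 weeks, the second is at week 16 or 18, no earlier than the first image. On the three-weekly schedule (second assessment week 18, image week 12) the simulated chance is 4.5 to 4.7% in every cell, which is simulation noise around 4.6%.

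**The case against.** **The 8-or-9-week interval may apply to MM.** It is the only general interval given, and the only row labelled as disease assessment in the MM tables is the marrow row. This is a fair point, and on that reading there is no bias. But 9 and 8 weeks are the lymphoma intervals stated in the same section, the MM tables contain no such visit, and Section 7.7 sends the reader to those tables. The per-cycle reading is better supported. Two readings that give different denominators are also a fault in a stopping rule.

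**The sponsor can wait or scan early.** Sections 3.1 and 3.4 speak of subjects having been assessed for response, the looks are approximate, and Section 7 lets assessment times be changed without an amendment. All true, but nothing requires a look to wait or an earlier scan to be done.

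**It belongs in the analysis plan.** The protocol itself defines this population and assigns it to the futility analysis, so the rule is already fixed here.

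**The yardstick should be the stated 8.5%.** Eleven of the 18 cells are at or below it. But 8.5% belongs to a look after every subject. For the three planned looks the like-for-like figure is 4.6%.

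**The model is simple.** It assumes that plasmacytoma subjects respond at the same 40% and that all other responders are confirmed by C3D1. This stands: late responders without a plasmacytoma would also be missed, so 4.6% is optimistic and the fix does not remove all bias. Allowing non-responders to fail early (median 8 weeks, 1 per week, 20% share) gives about 6.2% with no lag, 11.0% under the current rule and 7.3% with the fix.

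**The consequence is bounded.** The recommendation is not binding, later looks score these subjects correctly if enrolment continues, and the final ORR is untouched. This limits the weight of the point. However, Section 13.6.2 says that overriding a stop inflates the type I error, and more than half of the no-lag risk (2.7 of 4.6 points) arises at the first look.

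**Conclusion.** The concern holds. On the better-supported reading of Section 7.7, the evaluability rule admits ongoing subjects with a baseline plasmacytoma 6 weeks (three-weekly) or 8 weeks (weekly) before scheduled imaging can show PR, and this biases the interim response count downward.

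At a true ORR of 40%, the risk of a wrong futility recommendation rises from 4.6% to between 5.5% and 18.4% on the three-weekly schedule, and to between 5.7% and 23.1% if weekly dosing is used. The upper ends need both a 30% plasmacytoma share and 2 subjects per week. The protocol gives neither a share nor an accrual rate, so the direction is firm and the size is conditional. The effect is confined to subjects between C3D1 and C5D1 at a look, and an unscheduled earlier image would remove it for that subject. It is worth correcting but does not threaten the final analysis.

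**What to change.** - **Section 13.4.1:** state that an ongoing subject with a plasmacytoma at baseline is evaluable for futility only after two post-baseline disease assessments that include at least one post-baseline plasmacytoma image. Progression, death or permanent discontinuation continues to make a subject evaluable without this.
- **Section 13.6.2:** refer to the Section 13.4.1 definition instead of restating it, which also brings in the missing clause on progression, death and discontinuation.
- **Section 7.7:** limit the 8-or-9-week sentence to lymphoma and refer MM to the Time and Events Tables.

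The cost is wording in three sections and no extra scan. A look may wait for some subjects, by up to 6 weeks on the three-weekly schedule or 8 weeks on weekly dosing.
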